### 3.4 Analysis Visit Windowing Rules

The actual visit for a subject may not exactly coincide with their targeted visit date. The actual visit date will be mapped to the study visit following the analysis visit windowing rules below. Unless specified otherwise, all efficacy and safety analyses will be based on the analysis visits. If there are multiple records fall within the same defined analysis visit window, the non-missing record closest to the target day will be considered for the analysis.

If two non-missing assessment actual dates are equidistant from the target day, the later visit will be considered for analysis.

Composite endpoints (e.g. CDAI score) will be calculated for each date at which individual components are being measured before applying the analysis visit windows rather than to calculate visit window based individual component.

#### 3.4.1 DB Treatment Period

DB Period Study Day 1 is defined as the first day of DB IP administration. For subjects who are randomized but not dosed after randomization, the Day 1 is defined as the date of randomization.

DB Period Study Day is defined as the number of days from the Double-blind Treatment Period Study Day 1.

- Before DB Period Study Day 1:

Double-blind Treatment Period Study Day = (Date of Interest – Date of DB Period Study Day 1)

- On or After DB Period Study Day 1:

DB Period Study Day = (Date of Interest – Date of DB Period Study Day 1) + 1

Unless otherwise specified, all efficacy analysis will apply the analysis visit window rules as defined in [REDACTED]

[REDACTED]

[REDACTED]

[REDACTED]

### 3.4.2 OL Treatment Period

[figure not shown]
OL Period Study Day 1 is defined as the first day of OL IP administration. OL Period Study Day is defined as the number of days from OL Period Study Day 1.

- Before OL Period Study Day 1:

Open-Label Period Study Day = (Date of Interest – Date of OL Period Study Day 1)

- On or After OL Period Study Day 1:

OL Period Study Day = (Date of Interest – Date of OL Period Study Day 1) + 1.

## 3.5 Study Subjects

### 3.5.1 Subject Disposition and Completion Status

A summary of subject disposition throughout the study with respect to completion of double-blind induction and maintenance periods and open-label period will be provided. The number and percentage will be provided by treatment groups and overall using the randomized subjects as the denominator. The timing of and reasons for early withdrawal from treatment and from study will be tabulated and listed.

### 3.5.2 Demographics and Baseline Characteristics

Subject demographics and baseline characteristics will be listed for each subject. Following demographics and baseline characteristics will be summarized by treatment groups and overall using the ITT population. A summary of baseline disease characteristics may include, but not be limited to:

- Age
- Age (< 40 years, ≥ 40 years)
- Sex (Male, Female)
- Race (White, Black/African American, Asian, Other)
- Race (White, Non-white)
- Region (US, Non-US)
- Disease duration of CD (years)
- Disease duration (< 5 years, ≥ 5 years)
- Ethnic group (Hispanic or Latino, Other)
- Height (cm)
- Weight (kg)
- BMI (kg/m^2)
- Baseline disease location (ileum, not colon; colon, not ileum; or ileo-colonic, as observed at baseline ileocolonoscopy)
- Baseline CDAI score
- Baseline weekly abdominal pain score
- Baseline weekly loose/liquid stool count
- Baseline SES-CD score
- Baseline SES-CD score by baseline disease location subgroup (per subgroup of subjects with ileum, not colon; colon, not ileum; or ileo-colonic disease)
- Baseline CRP (mg/L)
- Baseline CRP (< 5 mg/L, ≥ 5 mg/L)
- Baseline fecal calprotectin (µg/g)
- Baseline fecal calprotectin (< 250 µg/g, ≥ 250 µg/g)
- Baseline fecal calprotectin (< 200 µg/g, ≥ 200 µg/g)

█

█

- Baseline IBDQ score
- Alcohol status (Never, Current and Former)
- Number of prior use of anti-TNF agents (1, > 1)
- Number of prior use of anti-TNF $\alpha$  agents (1, 2,  $\geq$  3)
- Prior use of vedolizumab (Yes, No)
- Use of 5-aminosalicylates at baseline (Yes, No)
- Use of corticosteroids at baseline (Yes, No)
- Use of immunomodulators at baseline (Yes, No)
- Smoking status at baseline (Never, Current, Former)

### 3.5.3 Study Drug Exposure

Descriptive statistics for extent of exposure (in days) will be presented for the safety population and the OL population during the specified treatment period.

For DB period, the following summaries will be provided using for the safety population:

- Duration of exposure in the DB period

For OL period, the following summaries will be provided using the OL population:

- Duration of exposure in the OL period

Additionally, descriptive statistics for the cumulative exposure for overall MEDI2070 will be provided. If a subject entered both the DB period and OL period, the subject will be considered as the same subject and the exposure data will be combined from both periods.

### 3.5.4 Prior and Concomitant Medications

*Prior medication* refers to all medications that were started prior to the start of the first dose of investigational product.

*Concomitant medication* refers to all medications taken during the treatment period of the DB period and the OL period. Concomitant medications include medications continued from pre-treatment.

Medications with missing start and stop dates will be counted as concomitant medications.

Medications with partial start or stop dates will be handled as described in Section 3.3.1. Medications with start and stop dates which bracket the first dose date will be flagged as both prior and concomitant medications.

All prior and concomitant medications data will be coded by World Health Organization Drug Dictionary, version March 2017 or newer and listed for each subject by treatment groups.

### **3.5.5 CD History**

The CD history will be listed using the safety population.

### **3.5.6 Medical and Surgical History**

Abnormalities in subjects' medical and surgical histories will be coded using the Medical Dictionary for Regulatory Activities (MedDRA), version 20.1 or newer. Preferred Term (PT) in the medical history and surgical history will be listed using the safety population.

### **3.5.7 Physical, Neurological and Visual Examination**

All data related to physical, neurological and visual examination will be listed for each subject.

### **3.5.8 Protocol Deviations**

Protocol deviations will be recorded and are classified as critical, major, and minor deviation. Listing of critical and major protocol deviations will be provided by treatment group.

## **3.6 Efficacy Analyses**

Efficacy data from the DB treatment period will be summarized descriptively by treatment group.

### **3.6.1 Primary Efficacy Endpoint(s) and Analyses**

#### **3.6.1.1 Primary Efficacy Endpoint**

The primary efficacy endpoint is Crohn's Disease Activity Index (CDAI) remission at Week 8. CDAI remission is defined as a CDAI score of < 150. Refer to [Appendix 6.1](#) for detail on CDAI score.

#### **3.6.1.2 Primary Efficacy Analysis**

The primary analysis will be conducted in the ITT population. The primary efficacy endpoint is CDAI remission at Week 8 of the induction period will be descriptively summarized.

#### **3.6.1.3 Additional Analyses of the Primary Efficacy Endpoint**

No sensitivity analyses of the primary efficacy endpoint will be performed.

## 3.6.2 Secondary Efficacy Endpoints and Analyses

### 3.6.2.1 Secondary Efficacy Endpoints

Remission and response will be assessed by both clinical and patient reported outcomes (PRO) measures. The following definitions will be used to define the secondary efficacy endpoints:

- CDAI clinical response: Decrease from baseline in the CDAI of  $\geq 100$  points
- SES-CD remission: Total SES-CD score  $\leq 4$ , with:
  - No subscore  $> 2$ , and
  - Segments scored at baseline that cannot be observed on a subsequent examination will be scored with an imputed value unchanged from baseline
- SES-CD response: Decrease from baseline in SES-CD  $\geq 50\%$ ; segments scored at baseline that cannot be observed on a subsequent examination will be scored with an imputed value unchanged from baseline.
- PRO2 remission (loose/liquid stool frequency/abdominal pain): Remission achieved for both abdominal pain and loose/liquid stool frequency
- PRO2 response: (loose/liquid stool frequency/abdominal pain): Remission or response in one symptom (either abdominal pain or stool frequency) plus response in the other
  - Abdominal pain remission: On an 11-point (0 to 10) pain scale: During 1 week, no daily score  $> 2$
  - Abdominal pain response: On an 11-point (0 to 10) pain scale:  $\geq 30\%$  reduction in weekly pain score from baseline
  - Loose/liquid stool frequency remission: Counting stools identified as Type 6 or 7 on Bristol Stool Form Scale, during 1 week, each daily loose/liquid stool count  $\leq 3$
  - Loose/liquid stool frequency response: Counting stools identified as Type 6 or 7 on Bristol Stool Form Scale,  $\geq 30\%$  reduction in weekly loose/liquid stool count compared to baseline

Please note that hematocrit results from hematology central lab testing during the study were required to calculate the CDAI scores for a given visit. It was discovered post-sponsor-transition in August 2017 that central labs for hematology were not required to be taken per protocol during study visits V8 (W20/D141), V9 (W24/D169), V11 (W32/D225), V12 (W36/D253), V14 (W44/D309) and V15 (W48/D337); therefore, the hematocrit item scores and subsequent CDAI total scores could not be calculated for these study visits. It was therefore agreed that any CDAI scores obtained from the study database for the above 6 visits will not be included in any study analyses. Refer to Note to File in [Appendix 6.3](#) for detail.

Refer to [Appendix 6.1](#) and [Appendix 6.2](#) for details on CDAI score and SES-CD score.

**Table 3-7 List of Secondary Endpoints**

Secondary Efficacy Endpoints		
Induction Period		
Week 8	PRO2 Remission Abdominal pain remission Loose/liquid stool frequency remission	PRO2 Response Abdominal pain response Loose/liquid stool frequency response CDAI clinical Response
Week 16	SES-CD Remission PRO2 Remission CDAI clinical remission Abdominal pain remission Loose/liquid stool frequency remission	SES-CD Response PRO2 Response CDAI clinical response Abdominal pain response Loose/liquid stool frequency response
Maintenance Period		
Week 28	CDAI clinical remission SES-CD Remission PRO2 Remission Abdominal pain remission Loose/liquid stool frequency remission	CDAI clinical response SES-CD Response PRO2 Response Abdominal pain response Loose/liquid stool frequency response

### 3.6.2.2 Secondary Efficacy Analyses

The efficacy data from the DB induction and maintenance periods will be summarized descriptively by treatment group and by visit using the ITT Population.

The secondary efficacy endpoints with dichotomous outcomes will be summarized similarly as the primary analysis of the primary efficacy endpoint using the ITT population.

### 3.6.2.3 Predictive Biomarker Analyses

*Due to a small number of subjects in the study, the predictive biomarker analyses will not be performed.*

## 3.6.3 Exploratory Efficacy Endpoints and Analyses

### 3.6.3.1 Exploratory Efficacy Endpoints

**Induction Period Exploratory endpoints:**

### **3.6.3.2 Analyses of Exploratory Endpoints**

Patient reported outcomes endpoints (e.g. change from baseline in IBDQ, change from baseline in newly developed PRO scores) will be described in Section 3.6.

The exploratory efficacy endpoints with continuous or ordinal outcomes (e.g. change from baseline in CRP and change from baseline in FCP) will be summarized descriptively.

### **3.6.4 Other Efficacy Analyses**

#### **3.6.4.1 Dose-Response Analysis**

*Due to a small number of subjects in the study, no dose-response analysis will be performed.*

#### **3.6.4.2 Efficacy Analysis for OL Treatment Period**

*Due to a small number of the subjects in the study, no efficacy analysis for OL Treatment Period will be performed.*

#### **3.6.5 Subgroup Analysis**

*Due to a small number of subjects in the study, no subgroup analysis will be performed.*

### 3.7 Patient Reported Outcomes

The study will utilize several PRO instruments. The sequence in which scoring instruments that contain PRO components (CDAI) or PROs will be collected at a given study visit will be the following order:

[figure not shown]
- CDAI
- Crohn's Disease Patient Reported Outcomes (CD-PRO)
- Inflammatory Bowel Disease Questionnaire (IBDQ)
- PGIC-IBD (Visits 7 and 10 only)
- Cognitive Patient Interview (selected subjects, Visit 10 or Early Termination Visit only)

[figure not shown]
Data from PGIC-IBD will be analyzed and reported separately (i.e. not in the clinical study report). Data from cognitive patient interviews was not available on account of early study termination.

The PRO data will be explored. A separate (supplementary) psychometric analysis plan (PAP) to explore the performance of the PRO instruments and to potentially develop new domain or total scores to inform endpoint development (including responder & remitter definitions) was developed by QuintilesIMS and the associated results will be reported separately in a psychometric analysis report (i.e. not in the clinical study report).

#### 3.7.1 CDAI score

The two items from CDAI, "total number of liquid or very soft stools over past week" and "total abdominal pain score over past week", will be descriptively summarized over time.

## **3.8 Safety Analyses**

The analysis of safety endpoints will include TEAEs, laboratory values, vital signs, and ECG. Only TEAEs and clinical laboratory evaluation from the 28-week placebo-controlled DB treatment period will be summarized using the safety population. All other safety endpoints will be listed. No statistical comparisons will be performed for the safety data.

### **3.8.1 Adverse Events and Serious Adverse Events**

Adverse events (AE) will be coded by MedDRA and the type incidence, severity and relationship to study investigational product will be summarized. Specific adverse events will be counted once for each subject for calculating percentages. In addition, if the same adverse event occurs multiple times within a particular subject, the highest severity and level of relationship observed will be reported. All AEs and SAEs collected in the database (including those starting prior to first dose of study drug) will be listed. Any other information collected (e.g. relatedness to study drug, action taken etc.) will be listed as appropriate.

#### **3.8.1.1 Pre-treatment AEs**

The AEs with onset prior to the administration of the first dose of investigational product (MEDI2070 or placebo) will be considered as pre-treatment AEs for the DB treatment period. Pre-treatment AEs will be listed with a flag.

#### **3.8.1.2 Treatment-Emergent AEs during DB Treatment Period**

For subjects entering the OL treatment period, the TEAE will be defined as any AE with onset on or after the administration of the first dose of blinded investigational product up to the day prior to administration of the first OL SC dose. For subjects not entering the OL treatment period, the TEAE will be defined as any AE with onset on or after the administration of the first dose of blinded investigational product up to and including 28 weeks post last blinded dose.

All TEAEs including TESAEs, Adverse Event of Special Interest (AESIs), and TEAEs leading to permanent discontinuation of investigational product will be summarized overall. The TEAEs with severity grades will be summarized by grades assigned by National Cancer Institute Common Terminology Criteria for AEs (NCI CTCAE) V4.0. Tabular summaries of the TEAEs during the DB treatment period will be provided as follows:

- Incidence rate of TEAEs by SOC and PT
- Incidence rate of TEAEs by SOC, PT, and severity
- Incidence rate of related TEAE by SOC and PT
- Incidence rate of TESIs by SOC and PT

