##### **4.8.5.1 Analysis of Adverse Events**

AEs will be monitored during the study and the data analyzed with respect to incidence within each treatment group as well as severity and potential relationship of the TEAEs to investigational product. The Medical Dictionary for Regulatory Activities (MedDRA) will be used to code all AEs. AEs with onset on or after the first dose of investigational product or with onset prior to the first dose of investigational product that increase in severity on, or after the first dose of investigational product will be considered treatment-emergent. TEAEs will be summarized by system organ class and preferred term. Tabular summaries of TEAEs will be provided as follows but not limited to:

- Incidence rate of TEAEs by treatment arm, system organ class, and preferred term

- Incidence rate of fatal TEAEs, TESAEs, TEAEs leading to permanent discontinuation of investigational product, treatment-related TESAEs, and AESIs will be provided
- Incidence rate of treatment-emergent and infectious AEs occurring in at least 5% of the subjects in any treatment arm by preferred term in descending order of frequency
- Incidence rate of TESAEs occurring in at least 1% of the subjects in any treatment arm

Analyses will also be performed for:

- Systemic hypersensitivity events; specific analyses will be performed for anaphylactic reactions
- Clinically significant infections; the frequency of serious infections, in particular GI infections, will be summarized for each treatment arm. For infections, whenever possible, the pathogen should be identified and recorded.
- Malignancies: events of malignancy will also be summarized for each treatment arm
- Infusion/injection-site reactions; the frequency of infusion/injection-site reactions will be summarized for each treatment arm
- Major cardiac events, defined as myocardial infarction, stroke, or cardiovascular death
- Ocular AEs, including cataracts; events of ocular AE, including cataracts, will be summarized for each treatment arm
- Surgery for CD: the time to onset of surgery for CD complications will be summarized for each treatment arm

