## **5 ASSESSMENT OF SAFETY**

### **5.1 Definition of Adverse Events**

The ICH Guideline for Good Clinical Practice E6(R1) defines an AE as:

Any untoward medical occurrence in a patient or clinical investigation subject administered a pharmaceutical product and which does not necessarily have a causal relationship with this treatment. An AE can therefore be any unfavorable and unintended sign (including an abnormal laboratory finding), symptom, or disease temporally associated with the use of a medicinal product, whether or not considered related to the medicinal product.

An AE includes but is not limited to any clinically significant worsening of a subject's pre-existing condition. An abnormal laboratory finding (including ECG finding) that requires medical intervention by the investigator, or a finding judged by the investigator as medically significant should be reported as an AE. If clinical sequelae are associated with a laboratory abnormality, the diagnosis or medical condition should be reported (eg, renal failure, hematuria) not the laboratory abnormality (eg, elevated creatinine, urine red blood cell

increased). Abnormal laboratory values that are not, in the investigator's opinion, medically significant and do not require intervention should not be reported as AEs.

AEs may be treatment emergent (ie, occurring after initial receipt of investigational product) or nontreatment emergent. A nontreatment-emergent AE is any new sign or symptom, disease, or other untoward medical event that begins after written informed consent has been obtained but before the subject has received investigational product.

Elective treatment or surgery or preplanned treatment or surgery (that was scheduled prior to the subject being enrolled into the study) for a documented pre-existing condition that did not worsen from baseline is not considered an AE (serious or nonserious). An untoward medical event occurring during the prescheduled elective procedure or routinely scheduled treatment should be recorded as an AE or serious adverse event (SAE).

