#### **5.4.1 Time Period for Collection of Adverse Events**

AEs will be collected from time that written informed consent is obtained until the end of subject participation in the study. New (nonserious) AEs that start after the reporting period has ended will not be collected. All AEs that start during the reporting period will be followed to resolution until the end of subject participation in the study.

All SAEs will be recorded from the time of informed consent.

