#### **3.9.1.1 Pre-treatment AEs**

The AEs with onset prior to the administration of the first dose of investigational product (MEDI2070 or placebo) will be considered as pre-treatment AEs for the DB treatment period. Pre-treatment AEs will be summarized with number of subjects and percentages by SOC and PT for each treatment group.

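### The final SAP defines TEAEs by onset alone and leaves out the protocol's rule that an AE present before first dose counts as treatment-emergent if it worsens afterwards

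*Combined protocol and SAP*

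**What the plan says.** Protocol section 4.8.5.1, on the analysis of adverse events, gives two routes to treatment-emergent status. One is onset on or after the first dose. The other covers AEs "with onset prior to the first dose of investigational product that increase in severity on, or after the first dose of investigational product".

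The final SAP (the one that records early termination) keeps only the first route. In section 3.8.1.2, "the TEAE will be defined as any AE with onset on or after the administration of the first dose of blinded investigational product". This appears in two sentences, one for subjects who enter the open-label period and one for those who do not. They differ only in where the window ends: the day before the first open-label dose, or 28 weeks after the last blinded dose. Section 3.8.1.1 assigns the rest: "The AEs with onset prior to the administration of the first dose of investigational product (MEDI2070 or placebo) will be considered as pre-treatment AEs", and "Pre-treatment AEs will be listed with a flag". Neither section makes an exception for worsening.

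The SAP written for the full study (sections 3.9.1.1 and 3.9.1.2) has the same onset-only definition, and its AEs with pre-dose onset also "will be considered as pre-treatment AEs for the DB treatment period". There they would have had their own table; in the final SAP they are only listed.

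Two other protocol sections bear on the point. Section 5.1 is looser than 4.8.5.1: "AEs may be treatment emergent (ie, occurring after initial receipt of investigational product) or nontreatment emergent". It adds: "An AE includes but is not limited to any clinically significant worsening of a subject's pre-existing condition". Section 5.4.1 fixes the collection period: "AEs will be collected from time that written informed consent is obtained until the end of subject participation in the study".

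**The concern.** The same event can be a TEAE under the protocol's analysis section and a pre-treatment AE under the SAP. The SAP describes itself as setting out the analyses that the protocol specifies. It says openly where it drops others because of the small number of subjects: predictive biomarkers (3.6.2.3), dose-response (3.6.4.1), open-label efficacy (3.6.4.2) and subgroups (3.6.5). Nothing of that kind is said about the TEAE definition.

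TEAEs and laboratory evaluations are the only double-blind safety data that section 3.8 still summarises. An event classed as pre-treatment would be missing from the four TEAE tables in section 3.8.1.2. It would also be missing from the overall summary of serious events, events of special interest and events leading to discontinuation. The rule in section 3.8.1 that reports a subject's highest severity does not bring it back, because a pre-treatment AE does not enter the TEAE tables.

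**Working it through.** The plan states no figure to reproduce, since the point concerns a definition. The check is to run each kind of AE through both rules.

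| AE | Protocol 4.8.5.1 | Final SAP 3.8.1.1 and 3.8.1.2 |
|---|---|---|
| Starts on or after first dose | TEAE | TEAE |
| Starts before first dose, no increase in severity | not a TEAE | pre-treatment |
| Starts before first dose, worsens after it, worsening entered as a new AE with its own onset | TEAE | TEAE |
| Starts before first dose, worsens after it, grade changed on the same record | TEAE | pre-treatment, listed only |

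Only the last row differs. Because AEs are collected from consent, that row holds only AEs that begin between consent and first dose and then worsen. At the start of the window, every AE that the SAP counts is also counted by the protocol, so the omission can only lower the counts.

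Partial dates narrow the gap a little further. Under final SAP Table 3-2, an AE with a missing start day in the month of Study Day 1 (or a missing day and month in that year) and a stop date after Day 1 is given Day 1 as its start. It then counts as a TEAE whether or not it really began earlier.

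The documents contain no AE data, so the number of affected subjects cannot be computed. The following shows scale only.

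- Inputs: 29 subjects randomised (final SAP section 2) and allocation 2:1:2:2:2, which sums to 9 (section 2.4).
- Expected arm size, if the 29 fell in that ratio: 29 × 2/9 = 6.44 in each of four arms, and 29 × 1/9 = 3.22 in the low-dose arm.
- Effect of one subject on a percentage: 100/6.44 = 15.5 points, and 100/3.22 = 31.0 points.
- With whole subjects: 100/7 = 14.3 to 100/6 = 16.7 points, and 100/4 = 25.0 to 100/3 = 33.3 points in the low-dose arm.
- Across all 29: 100/29 = 3.4 points.

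These shifts apply to a given row, by system organ class or preferred term, and only if the subject is not already counted there. Section 3.8.1 counts each specific event once per subject. A row for any TEAE would not move if the subject had another TEAE. The tables use dosed subjects, so actual denominators may be smaller than 29 implies.

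**The case against.** The strongest reply is that the mismatch begins inside the protocol. Section 5.1 separates AEs by whether they occur before or after first receipt of product, and the SAP follows that split. The protocol also leaves full analysis details to the SAP. This is fair as an account of how the gap arose. It does not remove it: section 4.8.5.1 is the explicit analysis rule, section 5.1 does not cancel it, and the SAP does not say that it chose one over the other.

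The second reply is that the effect may be nil. Section 5.1 makes clinically significant worsening of a pre-existing condition an AE, so sites may have entered a worsening as a new record, which the SAP already counts. This stands as a limit on size. The visible text does not say which recording convention was used, and the table specifications sit in a separate programming plan.

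The third is that nothing is hidden: all AEs, including those that start before dosing, are listed, and the pre-treatment ones are flagged. That also stands, and it keeps the priority low.

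A reader might go further and infer that the end of the TEAE window is also faulty, since section 3.8 speaks of a 28-week period while subjects who do not enter open label are counted to 28 weeks after their last blinded dose. The documents do not support that as a defect. The window matches the planned 28-week safety follow-up and is a legitimate convention.

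**Conclusion.** Wrong as written; low priority. The final SAP's TEAE definition conflicts with protocol section 4.8.5.1 and does not declare it. Confidence is high for the textual conflict, but not for any actual undercount: the number of affected subjects is unknown and may be zero. The shifts of about 16 and 31 points are what one subject could do to one row if the 29 fell in the planned ratio; they do not estimate bias.

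A reader might infer that events were lost from the report, or that the early-termination rewrite removed the worsening rule. Neither follows. The events remain in the listings, and the SAP for the full study already used onset alone.

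**What to change.** In each of the two sentences of final SAP section 3.8.1.2, add a second route: any AE that began before the first blinded dose and whose severity increases on or after that dose. Require the increase to fall within that sentence's existing window, up to the day before the first open-label dose or up to 28 weeks after the last blinded dose. Without that bound, a pre-dose AE that worsens during open-label treatment, or after follow-up ends, could be counted as a double-blind TEAE.

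In section 3.8.1.1, limit pre-treatment to AEs with pre-dose onset that do not increase in severity within that window. Check the open-label definition in section 3.8.1.3, which is also onset-only, for the same gap.

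If severity changes were not recorded with dates, the added route cannot be applied. In that case, state in the SAP that the definition departs from protocol section 4.8.5.1.

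The cost is small: a few lines of text and re-derived TEAE and pre-treatment flags, which feed the four tables, the overall summary and the flagged listing. Some counts may rise.
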